Aim 1a. To use GPS location data from CareConekta and spatial analysis to characterize peripartum mobility within the complete observational cohort (n=200), including the frequency, distance, and timing.

Outcome: Mobility within the study period

We will use data from all 200 participants to describe mobility within a complete observational cohort. In order to assess mobility comprehensively, we will use multiple data sources: time- and date-stamp data as well as geographic location data from CareConekta, participant self-report during questionnaires, and electronic medical records during the file review. Participant questionnaire data and medical record data will be exported from REDCap, and mobility data from CareConekta will be imported from .csv files to SAS for data analysis. To assess the primary outcome of interest, we will report the number of participants who travel during the study period (defined as >50 km for >7 days), over the denominator of all participants. Among those who travel, we will report the median and interquartile range number of trips during the study period and will determine timing and

frequency of travel as it relates to delivery date, which will be obtained from participant questionnaire and/or medical records. Median and interquartile range duration of travel will be reported in days, and we will also assess temporicity (frequency of trips x duration of trips). Reasons for travel will be obtained from the enrollment and follow-up questionnaire and will be grouped by theme, such as family, work, housing, and education.

For a more detailed assessment of mobility, we will use ArcMap to geographically place all locations in which participants were recorded during the study period. We will plot origin and destination locations on a map of South Africa, and neighboring countries (if necessary). We will connect origin and destination locations using ArcMap's XY-to-line tool, and will use a spherical calculator to estimate the distance between origin and destination. The geographic data will be used in conjunction with the novel metrics of mobility developed by [name], which are reflective of the complex forms of mobility in sub-Saharan Africa. For example, we will apply geopolitical boundaries to location codes so that measures of internal migration and localized mobility within and across those boundaries can be estimated, such as inter- and intra-provincial mobility. We also will map mobility flow according to origin and destination pairs, classified by geopolitical categories. We will thereby demonstrate how geographic data can be used to characterize the mobility of populations – providing a vital alternative to survey measures – in order to measure the impacts of that mobility on care cascade outcomes, with broad applicability to the measurement of its impact on other health outcomes. We also will conduct a secondary analysis to validate whether self-reported anticipated travel matches data collected from the CareConekta app.

Aim 1b. To assess the association between mobility and engagement in HIV care for mother (retention in care and viral suppression six months after delivery) and infant (completion of routine early infant diagnosis).

Outcome: Impact of mobility on engagement in HIV care in the absence of the intervention
We will limit the analysis to the control arm only to explore the impact of mobility on engagement in HIV care in the absence of intervention. We will report baseline participant characteristics as collected on the questionnaire. We will report proportions and 95% confidence intervals for categorical variables and medians and interquartile ranges for continuous variables. Open-ended questions will be reviewed for key themes. Themes will be abstracted and quantified.

To assess engagement in HIV care, we will report retention in care, which will be assessed at the six-month postpartum point and defined as no documented HIV-specific contact with any healthcare facility (including medication pick-ups) for >3 months. We also will report viral suppression six months after delivery, using thresholds of ≤ 50 and ≤ 1000 copies/ml. Additionally, we will report vertical HIV transmission and completion of the routine 10-week infant PCR test.

We will fit a series of models of mobility metrics on outcomes. For one, we will use a dichotomous exposure of mobility (any travel >50 km: yes/no), we will use Cox proportional hazard regression models to estimate the association of mobility on these outcomes, and will produce adjusted hazard ratios and 95% confidence intervals for retention in care and achieving viral suppression. We also will identify other predictors of engagement in HIV care. We will produce crude Kaplan-Meier curves to time to loss to follow-up and time to viral suppression by mobility group. Additionally, we will perform sensitivity analyses to explore how the estimated effect size changes when using varying cut-off points to define mobility.

Aim 2a. To assess the acceptability and feasibility of the standard and enhanced app, with a focus on identifying user preference and implementation outcomes.

Outcome: Acceptability and feasibility of CareConekta

Acceptability and feasibility data will be collected among all 200 participants. Those in the intervention arm will receive additional questions related to the enhanced app features. The outcomes selected for analysis in Aim 3a correspond with the Technology Acceptance Model for Resource-Limited Settings (TAM-RLS) framework, which was designed to draw attention to end-user acceptability as a predictor of mHealth technology adoption in low-resource settings.⁴⁶ We will report proportions and 95% confidence intervals for categorical variables and medians and interquartile ranges for continuous variables. For open-ended questions, we will create a list of categorical themes that emerge over multiple readings and calculate the proportions for the response categories. We will select key illustrative quotes for each theme.

Aim 2b. To evaluate the initial efficacy of the enhanced CareConekta intervention, using notifications and staff contact to improve engagement in HIV care, by assessing the association between study arm and engagement in HIV care at six-months postpartum.

Outcome: Efficacy of the intervention

The overall efficacy analysis will include participants in both arms (n=200). To assess overall cohort engagement in HIV care, we will report retention in care, which will be assessed at the six-month postpartum point and defined as no documented HIV-specific contact with any healthcare facility (including medication pick-ups) for >3 months. We also will report viral suppression six months after delivery based on the viral load test closest to the six-month period, using thresholds of ≤50 and ≤1000 copies/ml. Additionally, we will report vertical HIV transmission and completion of the routine 10-week infant PCR test.

Study arm assignment is the primary exposure of interest. We will use Cox proportional hazard regression models to estimate the association of study arm assignment on these outcomes, and will produce adjusted hazard ratios and 95% confidence intervals for retention in care and achieving viral suppression by study arm. We also will identify other predictors of engagement in HIV care. We will produce crude Kaplan-Meier curves to time to loss to follow-up and time to viral suppression by study arm. In a secondary analysis, we will perform an as-treated analysis using self-reported data regarding actually reading the notifications and/or WhatsApp messages or staff phone calls to analyze the effect of receiving the intervention.

HUMAN SUBJECTS' PROTECTION

Ethical review process

The research protocol will be reviewed by the Institutional Review Boards at Vanderbilt University; the University of California, San Francisco; and the University of Cape Town in South Africa. All research activities will occur in South Africa. All procedures will conform to U.S. and South African ethical standards for human subjects' research.

Informed consent

Informed consent will be obtained for all participants as described in the "Informed Consent" section above.

Privacy and confidentiality

Certainly the concept of tracing an individual's personal location is one that must address substantial protections of human subjects. First, our formative research with potential users in focus group discussions specifically addressed issues of privacy regarding a mobility-tracing app and notifications. For both issues, we found high acceptability.

While we feel that our formative research clearly indicates initial acceptability of mobility tracing and notifications, we have designed this work with a strong commitment to offering the highest level of protection of our participants' privacy and confidentiality. First, the location data of interest is at the macro-level, showing movement between towns, cities or regions, not at the micro-level, showing specific whereabouts. Thus, to protect participants' privacy, the transmitted location information will be made "fuzzy" by transmitting a random location within 1 km of each participant's exact location. Any participant's exact location within that radius will be unknown. All information collected by the app, including location, device ID and timestamp, will be transmitted to secure study servers using the secure https protocol. The participant's numerical study ID number will be used during installation; and no identifiable participant information will be recorded in the app.

Potential risks of the proposed research to participants and others

There is always the possibility of a breach of confidentiality of study materials when conducting research. While this is acknowledged, there is very low likelihood because of the precautions that will be taken to protect confidentiality. Study staff will be trained on the expectations that they are not to disclose any information collected in the study to anyone outside the study team. All identifying information associated with the study participants will be maintained in locked storage cabinets and complex password-protected computers that themselves are kept in locked rooms or cabinets. All participants will be encouraged to contact the clinic staff, principal investigators, or other staff to report any undesirable conduct associated with the study. These reports will be brought to the attention of the PI.

In the unlikely event that a study participant experiences or is involved in criminal activity that may relate to CareConekta mobility or user data, we will comply with all local laws regarding data handover.

Another risk to participants is that an HIV-positive status may be discerned through disclosure of participation in the study. However, we will do everything possible to minimize the risk of disclosure. We only will communicate with participants outside of the study if they do not return for their follow-up visit. No communication, whether on the phone or by text message, will identify the participant as HIV-positive. Importantly, among participants in the intervention arm who receive notifications of new facilities and phone calls and/or WhatsApp messages, the study staff will not use HIV-specific language. To avoid the possibility of inadvertent disclosure, ART facilities will only be referred to generically as "clinics" and any reference to ART will be to "tablets," a common term for any medication that we demonstrated was acceptable in an earlier mHealth study in South Africa.⁴⁴ We considered providing smartphones to all study participants, but felt that this might lead to inadvertent disclosure of HIV status through one's participation in the study, as well as potential issues related to coercion.

Additionally, discomfort or distress may arise from answering interview questions about behaviors or feelings. We will explain the nature of the questions to be asked during the consent process and all participants will be able to refuse to answer questions or terminate the interview at any time. Women who indicate psychological distress during study visits or interviews will be referred for support and counseling at the MOU. The interviews are designed to be supportive and non-confrontational and attempts will be made during administration of the study to minimize the discomfort of participants. Interviews will be conducted in private rooms with closed doors within the clinic that provide privacy for the participants. If an individual is uncomfortable during an interview, she will be reminded that she can terminate the interview and/or withdraw from the study at any time.

Risk to subjects will be minimized by: 1) training research staff in the ethical conduct of research; 2) strict protection of confidentiality by detailed standard operating procedures and on-site monitoring; 3) careful handling of sensitive data, procedures and processes in place to ensure data is securely stored and transferred; and 4) referral of participants to appropriate social and health services when necessary. The study site is well connected with the social worker and psychology services at the site as well as local non-governmental organizations providing counselling and support. While the potential risks to subjects are low, any social harm will be reported to the PI and a serious event will be reported to the Vanderbilt University and University of Cape Town IRBs within 48 hours of becoming aware of the event. Should any respondent experience discomfort or distress from participation in the study, we will provide the participant with the appropriate referral needed for follow-up and care.

Risk to subjects from participation in the study is minimal. All possible precautions will be taken to ensure complete confidentiality and protection of study participants. Given the minimal risk, the overall benefit of the study outweighs the risks.

Potential benefits of the proposed research to participants and others

The participants in the intervention arm who receive notifications while traveling may benefit from improved linkage to care while traveling and may have improved HIV-related outcomes. Moreover, the information obtained in this study will provide valuable information for future design and implementation of interventions aiming to improve retention in care among HIV-positive postpartum women. In addition, information obtained from participants will help inform our understanding of mobility among postpartum women and how it may contribute to HIV-positive women dropping out of care after pregnancy.

Data and safety monitoring plan

The study team will undergo extensive training prior to beginning the study, including training on issues of confidentiality. The PI has extensive experience with conducting research studies in South Africa and in training staff in the ethical application of research. In addition, the study team will be trained in ethical conduct of research.

The PI will monitor the study safety data on an ongoing basis. They will report to their IRBs and the South Africa HREC any breaches in confidentiality identified. In the event that a breach in confidentiality does occur, staff will be retrained on human subjects' protection and confidentiality if possible or removed from subject contact if the either the breach is too serious or if the PIs feel the staff member cannot be sufficiently retrained. Staff will be made aware of this condition on employment.

The PI will be responsible for reporting to the grant program director any action resulting in a temporary or permanent suspension of the research.

We will not convene a Data Safety Monitoring Board (DSMB) for this study.

Data accuracy and completeness

In addition to the co-investigators, the local South African study team will consist of a study coordinator, a site coordinator, and an interviewer/fieldworker. These team members will be trained in human subjects' research through the NIH's website or through a presentation developed by UCT faculty based on the NIH course, but adapted to the local context. Prior to contact with any subjects, all staff with participant interaction duties will be trained on the background and objectives of the study, procedures for obtaining informed consent, and correct administration of the questionnaire. Training will include procedures for minimizing risk to subjects, assuring data accuracy and protocol

compliance. The study team will also be asked to complete several practice interviews. To avoid bias and/or contamination, the study staff member who conducts interviews will not deliver the intervention calls and/or messages.

Participant remuneration

Following standards set by the University of Cape Town Research Ethics Committee, all participants will be reimbursed R150 (approximately US \$10.50) per study visit (enrollment and follow-up) for transport and missed opportunity costs. There will be no participant reimbursement for routine care visits made between study visits.

REFERENCES

1. Statistics South Africa. *Mid-Year Population Estimates 2018*. Pretoria; 2018. <https://www.statssa.gov.za/publications/P0302/P03022018.pdf>.
2. UNAIDS. *Global Report: UNAIDS Report on the Global AIDS Epidemic 2013*. Geneva; 2013. http://www.unaids.org/en/media/unaids/contentassets/documents/epidemiology/2013/gr2013/UNAIDS_Global_Report_2013_en.pdf.

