maximize the compatibility of CareConekta for the local context. Namely, we would like to transfer CareConekta's development architecture from the Ionic platform to native Android, so that we can ensure that CareConekta is compatible with all Android phones, which represents most smartphones in use by the population at the proposed study clinic. We will then be ready to pilot CareConekta to explore mobility and its impact on HIV care, and to conduct a preliminary evaluation of the enhanced CareConekta intervention.

STUDY POPULATION

Adult (≥ 18 years), HIV-positive, pregnant (≥ 28 weeks) women who 1) own a smartphone that meets the technical requirements, 2) are willing to opt-in to installation of CareConekta on her personal phone and mobility tracking, 3) demonstrate basic smartphone-level literacy, and 4) are willing to be randomized.

Technical requirements

For the purposes of this study, a smartphone will be defined as a mobile phone device with a touchscreen interface and internet and GPS capabilities. CareConekta is only available for phones using the Android operating system, version 5.0 or later. In our preliminary work, nearly 90% of smartphones of women approached for study participation used the Android system. Cell phone service providers must be one of the following: Vodacom, Cell-C, Telkom, or MTN. The phone must be able to demonstrate that it can use GPS by opening a map app, such as Google Maps, and finding current location. The phone must be capable of holding a battery charge; phones will be ineligible if they need to be charged more than twice per day on average (by self report).

INCLUSION AND EXCLUSION CRITERIA

Inclusion criteria:

- ≥ 18 years old
- HIV-positive
- Pregnant (≥ 28 weeks gestation)
- Able to speak and understand isiXhosa and/or English
- Currently own a smartphone that meets the technical requirements of the app
- Willing to opt-in to installation of the app on her personal phone and to mobility tracking
- Able to demonstrate basic smartphone-level literacy
- Willing to be randomized

Exclusion criteria:

- Currently enrolled in another research study which may impact on the study outcomes

STUDY TIMELINE

Study activities will occur from August 2019 – July 2022 (approximately)

Human subjects' participation will begin with recruitment and enrollment in approximately Q3 of Y1, following the adaptation and revision of the CareConekta smartphone app.

Activity	Year 1				Year 2				Year 3			

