The selection of participants will be equitable in relation to the research purpose and setting because any interested woman attending antenatal services at the study clinic who meets the eligibility criteria will be invited to enroll. Pregnant women will be limited by gestational age to the third trimester to allow for a nine-month total follow-up time within the time constraints of this three-year grant. In South Africa, most women present for their first antenatal visit around 20 weeks gestation or later,^{13,44,45} and attendance for antenatal visits is generally high,^{13,17} so we do not believe there will be substantial bias introduced by enrolling women later in pregnancy. isiXhosa is the predominant language in the region of the study site, and English also is widely spoken, so we do not anticipate excluding potential participants due to language. Basic smartphone-level literacy will be required of participants in order to assess the impact of messages. However, we anticipate that most women who own a smartphone already have a basic smartphone-level literacy ability. We acknowledge that women who own a smartphone may be different than those who do not, in terms of employment, education, or other factors. Besides the additional financial resources needed to provide phones, we want to be able to assess CareConekta in existing phones for maximal impact. If women already have a smartphone (over half of the population), providing a second phone for study purposes is redundant and burdensome. For women who do not already own a smartphone, we are concerned with ethical implications of providing such a highly-desired item as a smartphone in terms of possible coercion for study participation, the impact it may have on relationships between participants and partners and/or friends, and the potential for disclosure for participating in an HIV-related study.

In order to assess differences between our cohort of smartphone users and the general population assessed for eligibility, we will collect four demographic indicators at the time of recruitment: age, education, employment and nationality. These will be collected anonymously prior to study enrollment or the collection of any identifying data.

Informed consent

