Mobility data will be collected throughout the follow-up period. Geospatial coordinates will be recorded with a timestamp. Upon bulk extraction of these data, we will import location information as decimal degree coordinates into ArcMap spatial analysis software. Data charges related to the app are reverse-billed through our app development consultants to ensure timely transmission of data with no cost to participants.

Weekly raffle incentive

To encourage participants to keep the CareConekta app installed on their phone and the GPS function enabled throughout the entire study period, we will offer an incentive: a weekly raffle of one 200MB data bundle (worth approximately \$4). Participants will be eligible to enter the raffle if their phone sent GPS coordinates at least once per day for the prior week. Winners will be randomly selected among all eligible participants using a randomization code automated in STATA. The weekly raffle incentive will only apply to participants enrolled from October 2020 onwards and who have signed version 5.0 or later of the Informed Consent document. There is no limit to the number of times a participant may win the raffle.

Six-month postpartum follow-up visit procedures

Recontacting participant

All participants will be recontacted six months postpartum to return to the study site for a one-time visit. A minimum of three contact attempts by phone and/or home visit will be made for each participant. All contact attempts (successful or not) will be recorded on a contact log.

Follow-up questionnaire

Study staff will complete a face-to-face questionnaire with each participant. This follow-up questionnaire will include reasons for overall acceptability of CareConekta (standard or enhanced), reasons for travel and clinic switching, and barriers and facilitators to care since the start of the study. Response options primarily will be categorical, with open-ended questions to allow for deeper elaboration. Additional questions will be asked of participants in the intervention arm regarding acceptability and feasibility of the intervention. Responses will be recorded directly into a REDCap database by an interviewer using a tablet computer or laptop. This questionnaire may be conducted telephonically.

Viral load testing and potential blood draw

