In routine care in this setting, viral load tests are to be repeated every three months in pregnancy and every six months during breastfeeding, so we expect that most women will have a routine viral load completed before six months postpartum. To avoid additional blood draws for the participant, at the follow-up visit, the study staff will check NHLS to determine the most recent viral load test. If the participant has had no viral load test within 3 months prior to the six-month study follow-up visit, a blood draw for viral load will be conducted by the clinical staff at the Gugulethu CHC. A clinic nurse will collect 5 ml of venous blood, which will be transported daily to the National Health Laboratory Services (NHLs) for HIV viral load testing (Abbott Molecular RealTime HIV-1 assay (Abbott Molecular, Illinois, USA). We will not recontact participants about viral load results unless participants are on ART and the viral load result indicates lack of viral suppression. In that case, results will be made available to participants over the phone (or in person, at participant's wish) with appropriate referrals. For all participants, viral load results will be captured using the participants provincial folder number into the NHLs database, as is standard practice for routine laboratory results in South Africa.

Uninstall app

During the follow-up visit, the CareConekta app will be uninstalled from each participant's phone.

Reimbursement

After all the above steps are complete, the enrollment visit will conclude with providing the participant R150 reimbursement for transport and missed opportunity costs. Payment will be made in cash and/or grocery vouchers and will be recorded in a reimbursement log.

File review activities

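### Aim 1a summarises travel around delivery with no observation-time denominator, although women are observed for a short, varying antenatal period and about 26 weeks postpartum

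*Combined protocol and SAP*

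**What the plan says.** The Inclusion criteria require at least 28 weeks' gestation and give no upper bound. The section on equitable selection of participants gives the reason for third-trimester entry: "Pregnant women will be limited by gestational age to the third trimester to allow for a nine-month total follow-up time", set against the length of the grant.

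The end of observation is fixed relative to delivery. Under Recontacting participant, "All participants will be recontacted six months postpartum to return to the study site for a one-time visit". Under Uninstall app, "During the follow-up visit, the CareConekta app will be uninstalled from each participant's phone". Under Mobility data, "Mobility data will be collected throughout the follow-up period".

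Aim 1a in the analysis plan defines travel as more than 50 km for more than 7 days. It reports travellers "over the denominator of all participants". Then, among those who travel, "we will report the median and interquartile range number of trips during the study period". It also promises timing and frequency of travel in relation to the delivery date, plus trip duration. It draws on GPS, questionnaire self-report and medical records. It names no person-time denominator, no common window around delivery, no account of gestation at entry, and no rule for a trip that begins before delivery and ends after it.

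**The concern.** Aim 1a exists to describe the frequency, distance and timing of peripartum travel. Under these entry and exit rules every woman is watched for longer after delivery than before it, and the antenatal part differs from woman to woman. If the timing of travel is shown as counts of trips on each side of delivery, travel will look concentrated postpartum even when the weekly rate is the same throughout. The Introduction reports that women in earlier formative work mostly planned to travel after the birth, so readers may take such a pattern as confirmation.

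The ever-travelled proportion has a related weakness. A woman who enrols at 28 weeks has more time in which to be recorded as travelling than one who enrols near term. The proportion therefore reflects the enrolment pattern as well as travel, and would not transfer directly to a later trial with a different entry window.

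**Working it through.** **Inputs.** Entry at 28 weeks or later (Inclusion criteria). Observation ends six months postpartum (Recontacting participant, Uninstall app). Expected travellers are 25% of 200, that is 50 (Sample Size). The documents give neither the gestation at delivery nor the distribution of gestation at entry. I assume delivery at 40 weeks (37 to 42 tried) and show three entry patterns. One month is 365.25/7/12 = 4.348 weeks, so six months is 26.1 weeks, taken as 26.

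**The plan's own figure.** Follow-up = (delivery week − entry week) + 26. Entry at 28 weeks gives 12 + 26 = 38 weeks, and 38/4.348 = 8.7 months, which rounds to nine. The figure reproduces for the earliest entrants.

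**Other entry weeks, delivery at 40:**

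| Entry week | Antenatal weeks | Total weeks | Months |
|---|---|---|---|
| 28 | 12 | 38 | 8.7 |
| 32 | 8 | 34 | 7.8 |
| 36 | 4 | 30 | 6.9 |
| 40 | 0 | 26 | 6.0 |

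For entry at 28 weeks, delivery at 37 gives 9 + 26 = 35 weeks (8.0 months), and delivery at 42 gives 14 + 26 = 40 weeks (9.2 months). To reach 8.5 months with delivery at 40, a woman must enter by about 29 weeks. Under even entry over 28 to 40 weeks about 9% do.

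**Share of trips after delivery under a constant weekly rate** = 26 / (26 + mean antenatal weeks):

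| Entry pattern | Mean antenatal weeks | Postpartum share | Split of 50 trips (one each), post : ante |
|---|---|---|---|
| All at 28 | 12 | 26/38 = 68% | 34 : 16 |
| Even over 28–36 | 8 | 26/34 = 76% | 38 : 12 |
| Even over 28–40 | 6 | 26/32 = 81% | 41 : 9 |

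Mean follow-up is 34 weeks (7.8 months) in the second row and 32 weeks (7.4 months) in the third. With all entering at 28 weeks and delivery at 42, the share is 26/40 = 65%. If only trips completed within a period count, each window loses about a week because a trip must exceed 7 days; the shares become 25/36 = 69%, 25/32 = 78% and about 25/30 = 83%.

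**What a rate would show.** In the third row, 200 women give 200 × 6 = 1,200 antenatal and 200 × 26 = 5,200 postpartum woman-weeks. The unrounded 9.4 and 40.6 trips give 9.4/1,200 and 40.6/5,200, both 0.78 per 100 woman-weeks. The apparent excess disappears.

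**Ever-travelled.** Take the protocol's 25% as the value at 32 weeks. The constant weekly rate is −ln(0.75)/32 = 0.0090. Then 1 − exp(−0.0090 × 26) = 21% for a woman watched 26 weeks, and 1 − exp(−0.0090 × 38) = 29% for one watched 38 weeks.

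**The case against.** Several points on the other side stand.

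- A reader might infer that the nine-month figure is wrong. It is not: it reproduces for 28-week entry, and the sentence explains why women are not enrolled earlier, so it reads naturally as a ceiling.
- A reader might infer that the plan commits to comparing raw antenatal and postpartum counts. It does not say so. The word frequency leaves room for a rate, so this use of counts is inferred from silence.
- The 81% is the unfavourable end. The recruitment sections describe weekly screening of appointment lists, first visits from around 20 weeks, and generally high attendance. Many women could be enrolled soon after 28 weeks, which points towards 68%. Even that is more than two trips to one from window length alone.
- It is tempting to say that a woman enrolled at 39 weeks cannot complete an antenatal trip. That needs delivery by about 40 weeks; delivery at 41 would leave her 14 days.
- Past mobility is asked at enrolment (Table of schedule of measures). With no recall period stated this is partial cover, and Aim 1a's headline measures are confined to the study period.
- Describing mobility is the secondary objective of a pilot with no formal sample size, and the dates and coordinates are collected anyway, so rates could still be computed at reporting. This lowers the priority but does not remove the case for fixing the method beforehand.

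The plan's own reassurance about late enrolment concerns who is enrolled, not how long each woman is observed, so it does not answer the point.

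**Conclusion.** The point holds as a weakness in the stated Aim 1a summaries. Antenatal observation is short and varies by woman (0 to 12 weeks with delivery at 40; up to 9 with delivery at 37, up to 14 at 42), against about 26 weeks postpartum, and no summary accounts for this. With a constant travel rate and delivery at 40 weeks, about 68% to 81% of trips would fall after delivery from window length alone. The range rests on assumed entry patterns, because the documents give none. Ever-travelled would move from about 21% to 29% between the shortest and longest windows under the stated assumptions.

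The documents do not support extending this to the efficacy analysis. Randomization balances entry week between arms in expectation, so the Aim 2b comparison is not affected in expectation.

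**What to change.** In Aim 1a, keep the planned summaries and add the following:

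- Trips per 100 woman-weeks with GPS data, separately before and after delivery. Use weeks with GPS data and not the span from installation to uninstall: the raffle exists because continuous tracking is not assured, and a woman who misses the six-month visit has no staff uninstall date. Restrict the numerator to GPS-detected trips so that it matches the denominator, and report trips known only from self-report or records separately.
- A stated rule for trips that span delivery, for example assigning each trip to the period in which it starts and reporting how many span.
- Ever-travelled for the common window from delivery to six months postpartum, beside the whole-period figure and not in place of it, since late-pregnancy travel is part of the aim.
- The distribution of gestation at entry.

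In the section on equitable selection, describe follow-up as up to about nine months (about 6 to 9, depending on gestation at entry).

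Eligibility, visits and sample size do not change, and the time-stamped coordinates and delivery dates are already planned. The cost is a little more analysis work and imprecise antenatal rates: with about 9.4 antenatal trips, an approximate 95% interval spans a factor of exp(1.96/√9.4) = 1.9 either way.
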